5.1.2. General examination

A general clinical examination is required to assess eligibility. This examination will include demographics information, past medical ocular history, known allergies, and use of medications.

5.1.3. Fitzpatrick skin type

The Fitzpatrick skin type will be determined according to genetic disposition, reaction to sun exposure and tanning habits [28]. The Fitzpatrick scale classifies 6 skin types, as summarized in Table 1. In this study, only Fitzpatrick skin types I-IV are eligible to participate, consistent with the device labeling.

Revision: C State: Released ECO No: ca-00000172 Effective Date: 19-Sep-2019

5.1.4. Informed consent

During the informed consent (IC) process with the subject, the study investigator will explain the purpose of the study, the possible risks and benefits, and the schedule of visits required for participation. The study investigator will explain to the subject that, after signing the IC form, the subject may not be found eligible to participate in the study if he/she doesn't satisfy all inclusion/exclusion criteria.

The subject may take the IC form, consult with family, friends or doctor. After reading and understanding the IC, if the subject decides that he/she wishes to participate in the study, he/she should return within 1 week, with a signed IC form at which time he/she will undergo specific tests as specified below (sections 5.1.5 to 5.1.9). These tests will be done *only* after the subject signed the ICF, clearly indicating his/her understanding of the requirements and risks involved with study participation and other applicable treatment options.

5.1.5. Self-Assessment of Symptoms

To reduce the risk of bias, symptoms will be self-evaluated by the subject *before* any of the other specific tests (TBUT, MGS, and close-up photos of the eyelids) are performed by the study investigator(s).

Self-assessment of symptoms will be performed using 2 different methods:

- (1) Ocular Surface Disease Index (OSDI), using a questionnaire (developed by Allergan, Inc.) questionnaire. This questionnaire, which reports a single score for both eyes, is well-established for diagnosing symptoms of DED [30].
 - The questionnaire will be filled-out by the subject
 - The subject will grade 12 questions related to: ocular symptoms (3 questions), vision-related function items (6 questions) and environmental triggers items (3 questions)
 - Each of the 12 items will be scored from 0 to 4, where 0 indicates "never" and 4 indicates "always"
 - The questionnaire should take 5 minutes to complete.
 - OSDI will be calculated as the sum of the answered scores times 25, divided by the number of questions answered (range: 0 to 100).
 - Based on the OSDI, a subject can be categorized as having a normal ocular surface (0-12 points), mild symptoms (13-22 points), moderate symptoms (23-32 points), or severe symptoms (33-100 points), as described in [30].
 - OSDI at baseline is used for an inclusion criterion: to be included in the study, the subject must have OSDI ≥ 23 at baseline (moderate or severe symptoms).

QF-1044440 Rev. D	Global Clinical Study Report Template	GEN-0010523	Effective Date: July-2017

- (2) Eye Dryness Score (EDS), using a VAS. This questionnaire, which reports a single score for both eyes, has been used in other dry eye studies and was recently used as the primary symptom endpoint for FDA approval of lifitegrast for the treatment of signs and symptoms of dry eye (Xiidra, manufactured by Shire US, Inc.). EDS was accepted as a clinical outcome assessment by the division of transplant and ophthalmology at fda.gov (NDA 208073, June 2015)
 - The subject will be shown a 10 cm line, and will be asked to mark an X sign along the line
 - The subject will be instructed to mark the X sign on the leftmost side of the line if he/she does not have any symptoms of DED, on the rightmost side of the line if he/she has intolerable symptoms of DED, or somewhere along the line at a location that best represents his/her perception of symptoms in all other cases.
 - The distance between the left side of the line and the X mark will be measured. EDS (0-100) will be calculated as this distance times 10.

5.1.6.Assessment of TBUT

TBUT will be measured for each eye separately as follows:

- A FUL-GLO[®] fluorescein sodium ophthalmic strip (0.6 mg) will be applied to the inferior tarsal conjunctiva
- The subject will be asked to blink a few times to distribute the dye over the ocular surface.
- Once positioned at the slit lamp, the subject will close his/her eye completely.
- Then, the subject will be asked to open his/her eye without blinking.
- The timer will start as soon as the subject will open his/her eye, and it will be stopped at the first sign of breakup (first dark spot or discontinuity in the precorneal fluorescein-stained tear layer).
- For each eye, 3 consecutive readings will be taken.
- TBUT will be calculated as the average of these 3 readings.

TBUT at baseline is used as an inclusion criterion, and also to determine the identity of the study eye. To be included in the study, the study eye must have TBUT \leq 7 seconds at baseline (severity levels 2-5, as described in [31]). The study eye will be the eye with the lower TBUT at baseline (if both eyes have the same TBUT at baseline, see section 1).

5.1.7. Routine ophthalmic examination

Routine ophthalmic examinations will be performed separately for each eye, and will include: biomicroscopy with the slit lamp (examination of lid margins, meibomian gland orifices, eye lashes, conjunctiva, etc.), BCVA with an ETDRS chart, and IOP with tonometry.

Revision: C State: Released ECO No: ca-00000172 Effective Date: 19-Sep-2019

5.1.8. Assessment of MGS score

The MGS score will be estimated for each eye separately as described by Lane and colleagues [29]:

- Each gland will be graded as follows: 3 = clear liquid secretion, 2 = cloudy liquid secretion; 1 = inspissated/toothpaste consistency; 0 = no secretion.
- Along the lower eyelid, 15 glands will be evaluated: 5 nasal, 5 central and 5 temporal.
- MGS will be estimated as the sum of grades of these 15 glands (range: 0 to 45).

The MGS score at baseline will be used for an inclusion criterion: to be included in the study, the study eye must have MGS \leq 12 at baseline.

5.1.9. Close-up photos of the eyes

Close-up photos of both eyes will be captured with a high-resolution camera (> 325 ppi). Image resolution should be high enough to see the lid margins, the iris and individual eye lashes in focus.

For best results, the camera should be used in "Macro" mode. For a simpler camera with no macro mode (for example, iPhone 7), position the camera at a distance of 30-40 cm from the eye, and use the optic zoom to take a close-up photo. If a mobile phone camera is used, it is advised to use a second mobile phone to provide illumination, rather than rely on the flash capabilities of the camera. See an example in **Error! Reference source not found.** below.

Figure 7. Close-up photo of the eye

QF-1044440 Rev. D	Global Clinical Study Report Template	GEN-0010523	Effective Date: July-2017

Revision: C State: Released ECO No: ca-00000172 Effective Date: 19-Sep-2019

[figure not shown]
This photo was captured with an iPhone 7. The mobile phone was positioned at a distance of 30 cm from the eye. Zooming was performed by tapping on the screen with 2 fingers and using an outward spread gesture of the fingers. A second mobile as a source of illumination (instead of the flash mode).

5.1.10. Meibography

Meibography of the upper and lower eyelids in both eyes will be performed using an ophthalmic imaging device with a built-in infra-red camera, such as Lipiscan/Lipiview (TearScience/Johnson & Johnson), Keratograph 5M (Oculus), Antares (CSO/Lumenis) or equivalent system. While the patient rests his/her head on the chin rest, the eyelid will be gently everted (turned over) using a cotton tip applicator, and an image of the eyelid will be captured.

The percentage of area loss of the meibomian glands will be evaluated using a 5-point scale, as illustrated in Figure 8: 0: no loss; 1: < 25 % loss; 2: 26%-50\% loss; 3: 51%-75\% loss; 4: > 75% loss.

Area of Loss

Meiboscale

Figure 8. Five-grade Meiboscale

5.1.11. Enrollment

Subjects that passed all inclusion/exclusion criteria will be enrolled to the study and then randomized to the study arm or the control arm. After randomization, treatment may start

QF-1044440 Rev. D	Global Clinical Study Report Template	GEN-0010523	Effective Date: July-2017

immediately. At this time, subjects in the study arm may drop from the study if they fail to pass the test spots.

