For the first IPL treatment, the IPL settings are based on the results of the test spots. For the 1st test spot, it is advised to use the IPL settings recommended for treatment of shallow Rosacea/Telangiectasia (numbers in Table 2) and to examine the skin reaction after a few minutes. Upon decision of the study investigator, the IPL settings may be modified according to the ranges specified in Table 2. If the skin reaction to the 1st test spot is excessive (such as: a break in skin integrity, blistering, sloughing and/or discoloration or bruising), or if the IPL pulse is not well-tolerated, it is recommended to gradually decrease fluence, and/or gradually increase the delay Test spots can be repeated up to 5 times.

C	Lumenis Energy to Healthcare		
Description: LUM-VBU-M22-IPL-17-01_Protocol - Clinical study protocol for M22 Dry Eye			

For subsequent treatment sessions, test spots must be performed before the treatment itself. For the 1st test spot, it is advised to use the IPL settings used in the previous IPL session. The study investigator may slightly modify these settings depending on the long-term skin reaction or the efficacy of the treatment. If the long-term skin response obtained after the previous treatment session is excessive (such as: a break in skin integrity, blistering, sloughing and/or discoloration or bruising) the study investigator may *decrease* the intensity of treatment by decreasing the fluence by 1 J/cm², increasing the pulse duration by 1 msec and/or *increasing* the delay by 5 msec. On the other hand, if the long-term skin response is acceptable but the treatment was not effective, the study investigator may increase the intensity of treatment by *increasing* the fluence by 1 J/cm², *decrease* the pulse duration by 1 msec and/or *decrease* the delay by 5 msec. As for the first treatment, test spots can be repeated several times before the IPL settings are determined and the treatment itself can start.

Whether or not the IPL settings were modified from session to session, the IPL settings used for the treatment must be recorded in the appropriate eCRF.

Table 2. Recommended ranges of IPL settings.

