3.2. Subject Withdrawal and Replacement

In the written Informed Consent Form (ICF), the subjects will be advised that they have the right to withdraw from the study at any time without prejudice, and may be withdrawn at the Investigator's/Lumenis' discretion at any time. In the event that a subject drops out of the study or is withdrawn from the study, an Exit/Termination eCRF must be completed. On the withdrawal page the Investigator will record the date of the withdrawal, the person who initiated withdrawal and the reason for withdrawal.

Reasonable effort should be made to contact any subject lost to follow-up during the course of the study, in order to complete assessments and retrieve any outstanding data and study medication/supplies. The records of subjects who terminate prior to completing the study will be retained and the reason for termination will be documented.

The following are possible reasons for subject dropout/withdrawal:

- Adverse event that would prevent subject compliance with the protocol;
- Subject withdrawal of consent;
- Subject lost to follow-up (e.g., subject cannot be located or contacted and does not return for follow-up visits);
- Subject death;
- Investigator/Lumenis requested subject to be withdrawn.

Every effort will be made to follow the subject for the remainder of the study, even if the subject was withdrawn from the study.

DOC No.: 1009490

Revision: C State: Released ECO No: ca-00000172 Effective Date: 19-Sep-2019

Effective Date: July-2017

Revision: C State: Released ECO No: ca-00000172 Effective Date: 19-Sep-2019

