3.3.1. Screening and Baseline Assessments

The study investigator or a designee will start an informed consent (IC) process. The study investigator or a designee will explain that only subjects who sign the IC form are allowed to participate in this study. In the IC process, the subjects will be told that they have a 50% probability to be included in a study arm, and a 50% probability to be included in a control arm. Procedures in each of the arms will be explained to the subjects. The subject must understand that, after signing the IC form, further tests will be necessary to decide if he or she can continue in the study. The study investigator or a designee should clearly indicate that, even if the IC form is signed, the subject may not be allowed to participate in the study if the outcomes of some of the tests do not meet all inclusion and exclusion criteria, or if the immediate skin reaction to the test spots is not acceptable.

Following signing the IC form, the subject will first self-evaluate his/her symptoms using two tools: (1) the OSDI questionnaire; (2) the EDS, using a visual analog scale (0-100 VAS).

The following assessments will be performed in both eyes by a masked examiner:

• Three consecutive readings of TBUT (before any other test)

Revision: C State: Released ECO No: ca-00000172 Effective Date: 19-Sep-2019

- Routine ophthalmology tests, including:
 - Biomicroscopy with the slit lamp
 - Best-corrected visual acuity (BCVA) with an ETDRS chart
 - Intra-ocular pressure (IOP) measurement
- Meibography
- Number of non-atrophied meibomian glands in the lower eyelids
- Meibomian gland secretion score (MGS), using the method described by Lane and colleagues. [29]
- Capture of high-resolution photos of the upper and lower eyelids, including lid margins, irises and eyelashes

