4.1. Source and Sample Size

The aim of this study is to analyze up to 83 subjects (166 eyes) who completed the full schedule, randomized 1:1 to a study arm and a control arm. It is estimated that 23% of the subjects will be screening failures, and that 7%% of the randomized subjects will drop out or will be lost to follow-up. Therefore, to reach up to 83 subjects (166 eyes) who will complete the study,116 subjects are expected to be screened and 89 subjects are expected to be enrolled.

QF-1044440 Rev. D	Global Clinical Study Report Template	GEN-0010523	Effective Date: July-2017

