5.2.1. Pre-Treatment Procedures

- Before treatment, the subject's face must be thoroughly cleaned with a mild cleansing agent, like soap, facial wipes, or a medical grade alcohol diluted by 50%.
- The area to be treated will be coated with a thin (1-2 mm) layer of transparent coupling gel (provided by Lumenis).
- Both eyes of the subject must be completely occluded with protective goggles. The goggles must cover the entire peri-ocular region, including the upper and lower eyelids.
- In all subjects, several test spots (active IPL or sham IPL, depending on the arm) will be given in inconspicuous areas of the facial skin, for example on the lateral aspect of the malar region. In subjects of the control arm, these sham spot tests will have no function other than to mimic the actual treatment. In subjects of the study arm, these test spots will be used to determine the IPL settings.
- For the first treatment session, the IPL settings for the 1st test spot may be set using the values recommended in Table 2, or using less intensive settings at the discretion of the investigator(s). For subsequent treatment session, the IPL settings for the 1st test spot may be copied from the IPL settings used in the previous treatment session, unless the long-term skin reaction is not acceptable (including: a break in skin integrity, blistering, sloughing and/or discoloration or bruising). In this latter case the intensity of IPL settings for the 1st test spot should be reduced with respect to IPL settings used in the previous IPL session, either by decreasing the fluence, increasing the pulse duration, and/or increasing the delay.
- After each test spot, the investigator will wait a few minutes and then will examine the immediate skin reaction. If the skin reaction is acceptable and as expected (pinkish to red appearance of the skin, which should gradually fade within a few minutes), the IPL treatment
 QF-1044440 Rev. D Global Clinical Study Report Template GEN-0010523 Effective Date: July-2017

U Lumenis [®] Energy to Healthcare	
Description: LUM-VBU-M22-IPL-17-01_Protocol - Clinical s protocol for M22 Dry Eye	tudy

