5.4. Termination visit

Normally, termination should occur at the follow-up visit after all tests were performed. In case the subject shows excessive immediate skin reaction after several test spots, early termination can occur at any of the treatment visits. The reason for early termination should be documented in the termination eCRF. The Study Exit/Termination eCRF should be signed with the study investigator's signature.

6. Study Evaluations

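### Failing the test spots can take a subject out of the study after randomisation, in practice only from the IPL arm, and the plan does not secure that subject's follow-up visit or place in the primary analysis

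*Protocol*

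**What the plan says.** Protocol 3.3.1 lists, beside the inclusion and exclusion criteria, a further reason why a consenting subject might not take part: "or if the immediate skin reaction to the test spots is not acceptable". Read alone, this is an eligibility condition.

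Protocol 5.1.11 puts the test later. Eligible subjects "will be enrolled to the study and then randomized to the study arm or the control arm", treatment may follow at once, and at that point "subjects in the study arm may drop from the study if they fail to pass the test spots". Section 5.2.1 gives both arms test spots, but says of the control arm that "these sham spot tests will have no function other than to mimic the actual treatment". It also lets the investigator discontinue from the study a subject whose reaction remains unacceptable.

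The test is repeated. Protocol 2.5.6 says: "For subsequent treatment sessions, test spots must be performed before the treatment itself". Section 5.4 adds: "In case the subject shows excessive immediate skin reaction after several test spots, early termination can occur at any of the treatment visits".

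On what happens afterwards, Protocol 3.2 requires an exit form for anyone withdrawn and also states: "Every effort will be made to follow the subject for the remainder of the study, even if the subject was withdrawn from the study".

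SAP 3.3 bases the primary and secondary analyses on a per-protocol set that needs a follow-up visit and no major deviation. It defines an ITT set of all randomised subjects but gives that set no analysis. The adjusted sample size (Protocol 7.3.2, SAP 5.3.2) assumes that the final analysis is ITT.

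**The concern.** A condition that behaves like an entry criterion should act before randomisation, or act equally on both arms. This one does neither. A subject whose skin does not tolerate the spots can be identified only if allocated to IPL; the same kind of subject allocated to sham is never detected and stays in.

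If the IPL subject leaves without a follow-up TBUT, the analysis compares IPL-tolerant subjects with an unselected sham group. The investigator who decides also knows the allocation, since the sham filter carries a red label (Protocol Table 2). At stake is whether the estimated difference in TBUT change refers to the arms as randomised.

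**Working it through.** **Who can be removed, and when.** 3.3.1 treats the test spots like eligibility. 5.1.11 places them after randomisation and names only the study arm. The wording in 5.2.1 and 5.4 is not arm-specific, but the sham filter passes no light (3.8), so in practice only an active spot can produce the skin reaction that triggers removal. 2.5.6 and 5.4 extend this to all four treatment visits.

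**What happens to their outcome.** TBUT is measured after baseline only once, at follow-up. 5.1.11, 5.2.1 and 5.4 describe leaving the study; none asks for that visit. 3.2 does intend continued follow-up, but only as an effort. A subject without the visit is outside the per-protocol set. An ITT label would not by itself help, because the outcome in SAP 5.7.2 is the change from baseline, which cannot be formed without a follow-up TBUT, and neither document gives a missing-data method.

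**The plan's own figures.** Inputs (Protocol 7.3): mean changes 5 s and 1 s, SD 5 s, two-sided alpha 0.05, power 80%, 1:1.
- n per arm = 2 × (1.960 + 0.842)² × 5² / 4² = 24.5, so 25 per arm and 50 in total, as stated.
- Adjusted size, with between-eye correlation 0.5 and 8 of 34 IPL subjects responding as controls: SD of the two-eye mean = 5 × √0.75 = 4.33 s; mean difference = 4 × 26/34 = 3.06 s; variance in the IPL arm = 18.75 + 16 × (8/34)(26/34) = 21.63; SE = √((21.63 + 18.75)/34) = 1.09 s; power = Φ(3.06/1.09 − 1.96) = 0.80. The stated 68 reproduces, on an ITT basis.
- Enrolment: 83/0.93 = 89.2, stated as 89. That allows 89 − 83 = 6 losses in all, with 89/2 = 44.5 subjects per arm. The 7% is one pooled rate, not split by arm.

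**Size of the shift.** Let a share f of the IPL arm be lost, and let their TBUT change be g seconds smaller than that of the rest. The full-arm mean is then f × g below the mean of those retained, so the completer comparison is too large by f × g. With f = k/44.5 and g = 4 s (the assumed IPL mean less the control mean):
- k = 1: 0.09 s
- k = 2: 0.18 s
- k = 4: 0.36 s
- k = 6: 0.54 s

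Neither f nor g is in the documents, so a range is needed. The last two columns come from a simulation with no true IPL effect, 44 subjects per arm, SD 4.33 s and 40,000 runs. In it, subjects of the failing type change by g less in either arm and are removed from the IPL arm only. The nominal rate is 2.5%.

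| f | Shift, g = 2 s | Shift, g = 4 s | False win for IPL, g = 2 s | False win for IPL, g = 4 s |
|---|---|---|---|---|
| 5% | 0.10 s | 0.20 s | 3.1% | 4.1% |
| 7% | 0.14 s | 0.28 s | 3.5% | 4.7% |
| 13.5% (six of 44.5) | 0.27 s | 0.54 s | 4.6% | 7.7% |
| 20% | 0.40 s | 0.80 s | 6.0% | 11.4% |

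**What g means.** If g arises only because failing subjects go untreated while IPL works, it is zero when IPL has no effect, and the false-positive rate is unchanged. The inflation in the table needs failing subjects to have a poorer outlook whichever arm they are in. If g = 0 there is no shift; if they would have done better, the shift goes against IPL.

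**The case against.** The case on the other side has real force.

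- **Failure may be rare.** Up to five spots are allowed, with intensity reduced between them; darker skin types, photosensitising drugs and recent sun overexposure are excluded; discontinuation is permissive. This stands, and it limits the likely size.
- **5.4 and 3.2 do not contradict each other.** A reader might take the exit form in 5.4 to end follow-up. Section 3.2 itself pairs an exit form with continued follow-up, so follow-up is left unsecured, not forbidden.
- **Loss of TBUT is not certain.** A reader might infer it from the aim in 4.1 to "analyze up to 83 subjects (166 eyes) who completed the full schedule". That is a sample-size target, not an analysis rule.
- **Randomisation is not broken.** Allocation is intact and an ITT set is defined. What can lose its randomised basis is the analysed comparison, largely because SAP 3.3 makes per-protocol primary. But changing the set alone would not recover a TBUT that was never measured.
- **The direction is not known.** It is tempting to say that the bias favours IPL. That depends on g, which the documents do not give.
- **The triggering adverse event is not lost.** Protocol 8.1 records it, 8.1.5 follows it to resolution or for up to 6 months after the last treatment, and SAP 5.6.3 counts the first ocular event per subject. Only observations tied to later sessions, such as pain scores, are missing.

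None of this answers the central point: the filter operates after randomisation, in effect on one arm, and the plan does not secure the outcome of those it removes.

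**Conclusion.** The point holds as a gap in the plan that should be closed. Test-spot failure can remove IPL subjects after randomisation at any treatment visit, sham subjects cannot fail, and the primary analysis set requires a visit that the removal wording does not ask for. The analysed IPL arm can therefore be selected for tolerance of IPL when the sham arm is not.

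Size and direction are unknown. Under the stated assumption of a change 4 s smaller in those lost, the overstatement is about 0.09 s per subject. The 0.54 s figure needs all six planned losses to be IPL test-spot failures. Against the assumed 4 s difference this is small if failures are few. The finding does not rest on a contradiction between 5.4 and 3.2, on certain loss of TBUT, or on a known direction of bias.

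**What to change.** Reconcile Protocol 3.3.1, 5.1.11, 5.2.1 and 5.4 with 3.2, so that stopping device treatment after test spots is separate from leaving the study:

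- A randomised subject whose test spots are not accepted is asked, unless consent is withdrawn, to attend the scheduled follow-up visit (TBUT, OSDI, EDS, safety). The text should say how that visit is dated when fewer than four sessions took place.
- In 3.3.1, describe the test-spot reaction as something that may affect treatment after allocation, so that it no longer reads as an entry criterion.
- In SAP 3.3, assign the ITT set an analysis of the primary and secondary endpoints, as the sample-size section already assumes, with these subjects in their randomised arm. State how a missing follow-up TBUT will be handled.
- Report test-spot discontinuations by arm and visit.

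The decision whether to treat stays with the investigator, and no clinical rule is proposed. The cost is a few sentences in each document and follow-up visits for what may be a handful of subjects. The estimate may be slightly diluted by IPL subjects who received little or no treatment; the adjusted sample size already accepts dilution of that kind for the 8 subjects treated incorrectly.
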